## 15.3 Assessments During Treatment

### 15.3.1 Days 1-3 (Mandatory In-clinic)

The assessments or procedures listed below will be performed daily (unless otherwise specified) on Days 1-3 (see Section [15.3.4](#) for assessments/procedures required for discontinuation from the study).

- Study medication administration QID at 8 AM, 1 PM, 6 PM, and 11 PM.

- Effectiveness assessments at estimated time of maximum plasma concentration (Tmax, i.e., 3.5 hours after the first daily dose) including:
  - SOWS-Gossop; and
  - COWS.
- Completion of pre-defined withdrawal treatment goal (e.g., planned detoxification/transition) as assessed by the Principal Investigator (after completion of the SOWS-Gossop and COWS).
- Concomitant medication assessment.
- Vital signs including blood pressure and pulse at rest (sitting [or recumbent if necessary because of an AE]) and standing (if able) before every dose and 3.5 hours after administration of study medication at 8 AM, 1 PM, and 6 PM (7 times per day); respiration and temperature before 8 AM dose only.
- Continuous monitoring for AEs.
- 12-lead ECGs (in duplicate) before the first dose on Day 1 at 8 AM and 3.5 hours ( $\pm 15$  minutes) after dosing.
- A fingerprick blood sample for PK analysis will be collected concurrently with each scheduled ECG.
- Clinical laboratory tests as clinically warranted.
- Complete physical examination 3 to 4 hours after dosing on Day 1 and as clinically warranted.
- C-SSRS (Since Last Visit Version; [Appendix 6](#)) at 3.5 hours after the first dose (8 AM) on Days 1-3.
- A qualitative urine drug screening (by on-site use of “dipsticks”) will be done every day to monitor for contraband.

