### 15.3.2 Days 4-7 (In-clinic/Outpatient)

The assessments or procedures listed below will be performed daily (unless otherwise specified) on Days 4-7 (see Section [15.3.4](#) for assessments/procedures required for discontinuation from the study).

- Study medication administration QID at 8 AM, 1 PM, 6 PM, and 11 PM. Note that if subject is receiving outpatient treatment, he/she is required to take a dose of lofexidine in the clinic at each daily clinic visit.
- SOWS-Gossop 3.5 hours after the first daily dose during in-clinic treatment; once daily before an in-clinic dose of lofexidine during outpatient treatment.
- COWS 3.5 hours after the first daily dose during in-clinic treatment; once daily before an in-clinic dose of lofexidine during outpatient treatment.

- Completion of pre-defined withdrawal treatment goal (e.g., planned detoxification/transition) as assessed by the Principal Investigator (after completion of the SOWS-Gossop and COWS).
- Concomitant medication assessment.
- Pill count and review of subject diary ([Appendix 3](#)) to measure compliance with previous day's doses if being treated as an outpatient.
- Vital signs including blood pressure and pulse at rest (sitting [or recumbent if necessary because of an AE]) and standing (if able) during in-clinic treatment before every dose and 3.5 hours after administration of study medication at 8 AM, 1 PM, and 6 PM (7 times per day); respiration and temperature before 8 AM dose only.
- Vital Signs including blood pressure and pulse at rest (sitting [or recumbent if necessary because of an AE]) and standing (if able) during outpatient treatment before an in-clinic dose of lofexidine each day and 3.5 hours after dosing. Note that if the subject cannot stay in the clinic for measurement of the 3.5-hour post-dose vital signs required on Days 4-7, they will be given a portable digital blood pressure machine for measurement of their vital signs at this required time point. Subjects will also be provided a diary ([Appendix 3](#)) to record the measurements along with any symptoms of hypotension and/or bradycardia (see list in Section [13.2.2](#)) the subject may have experienced.
- A fingerprick blood sample will be collected during outpatient treatment when the subject reports to the clinic each day (before next scheduled dose) for analysis of plasma lofexidine concentration to monitor compliance.
- AE assessment.
- Clinical laboratory tests as clinically warranted.

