### **15.3.3 Days 8-14 (Outpatient Only)**

Study medication is optional on Days 8-14 for subjects continuing to have withdrawal symptoms per the Principal Investigator's judgment. The assessments and procedures listed

below will be performed daily (unless otherwise specified) (see Section 15.3.4 for assessments/procedures required for discontinuation from the study).

- Daily clinic visits and completion of subject diary.
- SOWS-Gossop before an in-clinic dose of lofexidine.
- COWS before an in-clinic dose of lofexidine.
- Completion of pre-defined withdrawal treatment goal (e.g., planned detoxification/transition) as assessed by the Principal Investigator (after completion of the SOWS-Gossop and COWS).
- Concomitant medication assessment.
- Pill count and review of subject diary ([Appendix 3](#)) to measure compliance with previous day's doses.
- Vital Signs, including blood pressure and pulse at rest (sitting [or recumbent if necessary because of an AE]) and standing (if able) before an in-clinic dose of lofexidine and 3.5 hours after dosing on Days 8-13 and once before any dose on Day 14. Note that if subjects cannot stay in the clinic for measurement of the 3.5-hour post-dose vital signs required on Days 8-13, they will be given a portable digital blood pressure machine for measurement of their vital signs at this required time point. Subjects will also be provided a diary ([Appendix 3](#)) to record the measurements along with any symptoms of hypotension and/or bradycardia (see list in Section 13.2.2) the subject may have experienced.
- AE assessment.
- Clinical laboratory tests as clinically warranted.
- Complete physical examination as clinically warranted.
- C-SSRS (Since Last Visit Version; [Appendix 6](#)) before an in-clinic dose of lofexidine.
- A fingerprick blood sample will be collected during outpatient treatment when the subject reports to the clinic each day (before next scheduled dose) for analysis of plasma lofexidine concentration to monitor compliance.
- Qualitative urine drug screening (by on-site use of "dipsticks") will be done every day in an outpatient setting to monitor for illicit drug use.

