#### *Vital Signs Measurements*

Summary statistics for observed and changes from baseline in sitting and standing vital signs, separately, will be tabulated at each follow-up for each vital sign parameter and at post-baseline endpoint for each variable overall and for each co-administration category. All values will be included in the summary of potentially clinically significant vital signs. However, post-baseline repeat/unscheduled assessments will be excluded for the other tabulations.

In addition the number and proportion of subjects having PCS will be tabulated:

- Systolic blood pressure  $\geq 180$  mmHg and an increase of  $\geq 20$  mmHg from baseline
- Systolic blood pressure  $\leq 90$  mmHg and a decrease  $\geq 20$  mmHg from baseline;
- Diastolic blood pressure  $\geq 105$  mmHg and an increase  $\geq 15$  mmHg from baseline;

- Diastolic blood pressure  $\leq 50$  mmHg and a decrease  $\geq 15$  mmHg from baseline; or

Additionally, the number and proportion of subjects having a dose-hold due to a VS measurement will be tabulated as follows:

Resting (sitting [or recumbent if necessary because of an AE])

- Systolic blood pressure  $<90$  mmHg and  $>20\%$  below screen value;
- Diastolic blood pressure  $<50$  mmHg and  $>20\%$  below screen value;
- Pulse  $<50$  bpm and  $>20\%$  below screen value; or
- Symptoms of hypotension and/or bradycardia (e.g., lightheadedness, dizziness).

Orthostatic (after standing for 3 minutes)

- Systolic blood pressure diastolic blood pressure, or pulse  $>25\%$  below recumbent values.

In addition, the number and proportion of subjects meeting the discontinuation Vital Signs criteria will be tabulated as follows:

- Resting systolic blood pressure  $<70$  mmHg;
- Resting diastolic blood pressure  $<40$  mmHg;
- Resting pulse  $<40$  bpm;
- QTcF  $>500$  msec or  $>25\%$  above screen value for both males and females; or
- Syncope.
- Persistent symptomatic hypotension (e.g., hypotension not responding to bed rest or fluids).
- Single occurrence of symptomatic bradycardia (as assessed by Principal Investigator/study physician/assigned staff, regardless of blood pressure) associated with chest pain, shortness of breath, or decreased level of consciousness.

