- Persistent hypertension – resting blood pressure  $\geq 185/110$  mmHg recorded on 3 separate occasions taken at least 5 minutes apart AND within a 1-hour time period. If 2 of 3 readings are  $\geq 185/110$  mmHg (either systolic  $\geq 185$  mmHg or diastolic  $\geq 110$  mmHg) the subject must be discontinued.

All of the above will be summarized overall and for each co-administration category at each study day.

The incidence of missed standing vital signs will be counted for those subjects with a resting blood pressure measurement and a missing standing blood pressure measurement. The count of unique subjects and number of events will be tabulated. Consecutive missing measurements will be counted as one event. Additionally, the number of missed doses and the reason for each missed dose will be presented for each subject and study day.

The number and percentage of subjects with a reduced dose that still met each of the above criterion after the dose reduction will be presented overall and for each co-administration category by study day.

Mean profiles by study day will be presented for sitting and standing blood pressure and pulse rate.

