#### **Section 6.10 Adverse Events**

Change: Addition of adverse event summaries by inpatient and outpatient phase.

Reason: There is interest in the difference between inpatient and outpatient events.

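### The by-day vital-sign threshold proportions in SAP 6.9 mix risk with measurement frequency, because scheduled readings fall from 7 a day in clinic to 2 a day as an outpatient

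*SAP*

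**What the plan says.** **Tables.** SAP 6.9 (Vital Signs Measurements) plans three threshold tabulations. The first covers potentially clinically significant (PCS) systolic and diastolic values: "In addition the number and proportion of subjects having PCS will be tabulated". The second counts subjects with a dose hold due to a vital sign. The third counts subjects meeting discontinuation criteria. The closing instruction is: "All of the above will be summarized overall and for each co-administration category at each study day". For the PCS table, "All values will be included in the summary of potentially clinically significant vital signs"; repeat and unscheduled readings are left out of the other vital-sign tabulations.

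The SAP sets no common number of readings or matched time point for these tables, prints no reading count and does not split them by setting. It does plan an inpatient/outpatient split for C-SSRS and for adverse events. For adverse events, SAP 6.10 gives the reason: "There is interest in the difference between inpatient and outpatient events".

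**Schedule.** For in-clinic days, Protocol 15.3.1 lists "Study medication administration QID at 8 AM, 1 PM, 6 PM, and 11 PM" and requires blood pressure and pulse "before every dose and 3.5 hours after administration of study medication at 8 AM, 1 PM, and 6 PM (7 times per day"). Section 15.3.2 keeps this for subjects who stay in clinic on Days 4-7. Those who leave are measured "during outpatient treatment before an in-clinic dose of lofexidine each day and 3.5 hours after dosing". In Days 8-14 everyone is an outpatient, measured "before an in-clinic dose of lofexidine and 3.5 hours after dosing on Days 8-13 and once before any dose on Day 14" (Protocol 15.3.3). Footnote (m) of the assessment schedule, in both documents, adds a set at the end-of-treatment or discontinuation visit. Protocol 13.2.2 applies the dose-hold criteria to pre-dose vital signs.

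**The concern.** The SAP does not spell out when a subject counts on a given day. A proportion of subjects per day is naturally read as the share with at least one qualifying reading that day, and that share rises with the number of readings taken. The number of readings changes with setting, and setting changes with study day. So the by-day rows carry measurement frequency as well as risk, and the rows for Days 4-7 pool subjects on 7 sets with subjects on 2.

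The primary objective is safety in both in-clinic and outpatient settings, and the study is descriptive, so these tables are part of its main output. A fall in threshold incidence after Day 3 could be read as adaptation to the drug or as outpatient safety when part of it is only less frequent measurement.

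**Working it through.** **1. Reproduce the plan's own count.** In clinic there are 4 pre-dose sets (one per dose) and 3 sets at 3.5 hours (after the 8 AM, 1 PM and 6 PM doses): 4 + 3 = 7, which matches the protocol's stated figure.

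**2. Apply the same count elsewhere.**
- Day 1: the first set is taken before any drug (Protocol 15.2), so 7 - 1 = 6 are on drug. SAP 6.2 uses the last screening value as the vital-sign baseline, so nothing there removes the Day 1 pre-dose set from the Day 1 row.
- Outpatient, Days 4-13: 1 + 1 = 2.
- Day 14: 1 pre-dose set, plus an exit-visit set if that falls on the same day.
- Scheduled pre-dose checks for dose holds: 4 in clinic, 1 as an outpatient.

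**3. Hold risk constant and vary only the count.** Let p be the chance that one reading meets a criterion and k the number of readings. Neither p nor the within-day correlation is in the documents. I assume p = 5% for the main illustration, with 1% to 10% as the range, and ICC from 0 to 0.8.

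Independent readings: P(at least one) = 1 - (1 - p)^k.

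Correlated readings (beta-binomial): P = 1 - B(a, b + k) / B(a, b), where B is the beta function, a = p(1 - ICC)/ICC and b = (1 - p)(1 - ICC)/ICC.

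At p = 5%:

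| ICC | k = 7 | k = 2 | k = 1 | ratio, 7 to 2 |
|---|---|---|---|---|
| 0 | 30.2% | 9.8% | 5.0% | 3.1 |
| 0.2 | 20.0% | 8.8% | 5.0% | 2.3 |
| 0.5 | 12.3% | 7.4% | 5.0% | 1.7 |
| 0.8 | 7.5% | 6.0% | 5.0% | 1.3 |

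Hand checks: 1 - 0.95^7 = 0.302. At ICC 0.5, a = 0.05 and b = 0.95, so k = 2 gives 1 - (0.95 × 1.95)/2 = 0.074.

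For other p with independent readings, 7 against 2 gives 6.8% against 2.0% (p = 1%), 13.2% against 4.0% (p = 2%) and 52.2% against 19.0% (p = 10%).

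**4. Pre-dose checks, 4 against 1, at p = 5%.** 18.5% against 5.0% (ICC 0), 10.1% against 5.0% (ICC 0.5), 6.8% against 5.0% (ICC 0.8).

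**5. Dilution on Days 4-7.** If a share s are outpatients, the pooled row is (1 - s) × P(k = 7) + s × P(k = 2). At p = 5% and s = 25, 50, 75 and 100%, this is 25.1, 20.0, 14.9 and 9.8% at ICC 0, against 30.2% with everyone on 7 sets. At ICC 0.5 it is 11.1, 9.9, 8.6 and 7.4%, against 12.3%.

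**6. Matched count.** With one pre-dose and one 3.5-hour set in both settings, k = 2 throughout, and constant p gives 9.8% against 9.8% at ICC 0. Pre-dose only, for Day 14, gives 5.0% against 5.0%.

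**The case against.** The strongest case against has several parts.

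- **Independence overstates the effect.** Readings in one subject on one day are likely to be correlated, and the ratio then shrinks from 3.1 to as little as 1.3 in the table. This stands, so the independent figure should not be quoted alone.
- **The three tables are not equally exposed.** Of the eight discontinuation items, four (QTcF, syncope, persistent symptomatic hypotension, symptomatic bradycardia) do not depend on the number of scheduled sets, and meeting a discontinuation criterion removes the subject, so it is not a repeated daily risk. Dose holds need confirmation under the 2-of-3 rule (Protocol 10.4), can be triggered by symptoms, and for outpatients can follow a telephone call (13.2.2). This stands as a limit on scope. Confirmation lowers the risk per check but does not equalize the number of checks.
- **Other planned output helps.** SAP 6.9 also summarizes values and changes at each follow-up, and gives mean profiles by day. These describe averages, so they are a partial check and do not replace threshold counts.
- **No match is exact.** The outpatient set precedes a clinic dose at whatever hour the visit falls; Protocol 12.2 allows a morning visit followed by one the next afternoon. The in-clinic 8 AM set comes 9 hours after the 11 PM dose, while a 1 PM set comes 5 hours after the 8 AM dose. The outpatient post-dose set may be self-measured at home, with a ±30 rather than ±15 minute window (15.5.2). This stands: the 8 AM pair is an approximation.
- **A decline has other causes.** Hypotensive sensitivity informs the move to outpatient care (13.2.1), subjects drop out, and doses taper on Days 8-14. Matching readings removes none of these, but that is no reason to keep an avoidable artefact that can point the same way.

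**Conclusion.** The concern holds as a confounding of daily threshold incidence with measurement frequency. The reading counts are certain from the schedule. The size is not: at 5% per reading, the 7-to-2 ratio runs from 3.1 (independent) to 1.3 (ICC 0.8), and it disappears only when readings within a day are almost perfectly correlated. These figures assume the same risk at every reading and a subject-level count of at least one qualifying reading a day.

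A reader might infer more than the documents support:

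- *That a sharp drop after Day 3 is bound to appear, or that any drop is artefact.* The step is diluted on Days 4-7 by subjects still in clinic, and its size rests on assumed values.
- *That Day 14 always has a single set.* An exit-visit set may fall on that day. Day 7 can also be short, because subjects may leave after one dose.
- *That the PCS table would show bradycardia falling.* It has no pulse criterion; bradycardia enters only through the dose-hold and discontinuation tables.
- *That the inpatient/outpatient adverse event comparison is always tilted one way.* Threshold-meeting values must be recorded as adverse events (Protocol 10.4, 15.5.2), so frequency does matter there. But scheduled sets per phase are 3 × 7 = 21 on Days 1-3 against 4 × 2 = 8 for an outpatient on Days 4-7, and 8 + 6 × 2 + 1 = 21 for an outpatient through Day 14.

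**What to change.** In SAP 6.9:

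1. Split the by-day threshold tables by setting on Days 4-7.
2. Keep the all-readings tables, but print the number of subjects and the number of readings beside each proportion.
3. Add a version of the blood pressure and pulse threshold tables limited to one scheduled pre-dose set and one 3.5-hour post-dose set per subject-day. In clinic, use the 8 AM pair as an approximate match. Treat the Day 1 pre-dose set as untreated. For Day 14 use the pre-dose set only, with any exit-visit set shown separately.
4. Base day-to-day and in-clinic/outpatient statements on the restricted version. State that selection into outpatient care, dropout, the Day 8-14 taper, visit time and home measurement still limit the comparison.
5. Add a note to the inpatient/outpatient adverse event tables that threshold-based hypotension and bradycardia events depend on how often vital signs were measured. A formal split of adverse events by vital-sign trigger should not be required, because the documents describe no data field for it.

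The cost is SAP wording and a few extra tables, with no new data and no change to study conduct. The restricted version uses fewer in-clinic readings and will show fewer events, which is why the all-readings tables stay.

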#### *ECG*

For ECG data collected during this study, a separate SAP will be used for the analysis and the results will be presented separately in a stand-alone report.

In addition, PI overall interpretation of the ECG (Normal, Abnormal NCS, and Abnormal CS) will be listed in [Appendix 16.2](#).

#### *Clinical Laboratory Evaluations*

Descriptive statistics will be calculated for the baseline values, study discontinuation values and for the changes from baseline for each continuous hematology, coagulation, chemistry and urinalysis parameter. Each measurement will be categorized as below, within, or above normal range, based on ranges supplied by the laboratory used. Shift tables in relation to the normal range from baseline to study discontinuation will be presented. For post-baseline laboratory values, only scheduled values will be tabulated. Post-baseline repeat/unscheduled assessments will be disregarded, although they will be listed in the relevant appendices to the report; in particular all clinically significant values will be noted in a table or a separate listing.

Details of clinically warranted clinical laboratory tests and microscopic urinalysis will be provided in [Appendix 16.2](#) of the report.

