#### 15.5.4 Clinical Laboratory Evaluations

##### 15.5.4.1 Standard Laboratory Tests

Standard clinical laboratory safety evaluations (see [Table 3](#)) will be performed for all subjects at screening, as needed at the study physician's discretion throughout the study, and at discontinuation from the study. For this multicenter study, a central laboratory will be used that is directly accredited by the College of American Pathologists (CAP) and licensed by the Clinical Laboratory Improvement Act of 1988 (CLIA); both certification and accreditation must be renewed every 2 years. The laboratory will need to provide a copy of current certification and provide the normal values for all analytes to determine the upper limit of normal (ULN).

Table 3. Hematology, Chemistry, and Urinalysis Tests

Hematology (a)	Chemistry (b)	Urinalysis
Hemoglobin	Cholesterol	Color
Hematocrit	Triglycerides	Clarity
Red blood cell (RBC) count	Sodium	pH
MCV	Potassium	Specific gravity
MCH	Chloride	Protein
MCHC	Carbon dioxide (CO 2 )	Glucose
RDW	Glucose	Ketones
White blood cell (WBC) count	Creatinine	Bilirubin
WBC differential (% and Abs)	Albumin	Nitrite
neutrophils	Total protein	Blood
lymphocytes	Calcium	Urobilinogen
monocytes	Phosphorus	WBC
eosinophils	Aspartate aminotransferase (AST)	RBC
basophils	Alanine aminotransferase (ALT)	Epithelial cells
Prothrombin time (PT)	Gamma-glutamyl transpeptidase (GGTP)	Bacteria
aPTT	Total bilirubin	Casts
Platelet Count	Lactate dehydrogenase (LDH)	Crystals
	Alkaline phosphatase	
	Blood urea nitrogen (BUN)	
	Thyroid-stimulating hormone (TSH)	
	Free thyroxine (T4)	

**Abbreviations:** Abs = absolute; aPTT = activated partial thromboplastin time; MCH = mean corpuscular hemoglobin; MCV = mean corpuscular volume; MCHC = mean corpuscular hemoglobin concentration; RDW = red blood cell distribution width

- (a) Blood will be collected in anticoagulant containing evacuated venous blood collection tubes (e.g., VacutainerTM).
- (b) Blood will be collected in serum separation evacuated venous blood collection tubes (e.g., VacutainerTM) and serum separated according to standard procedures.

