## 6.2 Derived Data

- Definition of baseline

With the exception of vital signs measurements, baseline is defined as the last non-missing value prior to the receiving the first dose of study medication. For vital signs measurements, the last screening measurement will be used as baseline.

All tabulations involving change from baseline data will only include subjects with cohort data i.e. with data at baseline and at follow-up. Change from baseline will be calculated as follow-up values minus baseline value.

- Incomplete dates

All incomplete dates will be included in the clinical database as they were entered in the eCRF. Thereafter for calculation purposes, the incomplete dates will be completed using pre-defined rules. If a day or month is not recorded it will be replaced by the first day of the month or January respectively, provided this does not contradict any other dates recorded. For missing adverse events and medications dates/times during the trial, the worst-case date will be used (e.g. the end of the month for a stop date and 23:59 for the stop time, the date/time of initial dose for start of AE i.e. all events with missing start dates will be assumed to be treatment emergent).

- Ambiguous values

In the case where a variable is recorded as “ $>x$ ”, “ $\geq x$ ”, “ $<x$ ” or “ $\leq x$ ”, then for analysis purposes a value of x will be taken. Where a range of values is quoted the midpoint of the range will be taken.

- Questionnaire Data

In the event that component items used to calculate total scores for questionnaire data e.g. SOWS Gossop score are missing then the total scores will also be set to missing.

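### Laboratory tables take scheduled post-baseline values only, and the one scheduled test is at exit, so out-of-range results on as-needed tests during treatment are not counted in them

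*SAP*

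**What the plan says.** Protocol 15.5.4.1 sets the laboratory schedule. Standard tests "will be performed for all subjects at screening, as needed at the study physician's discretion throughout the study, and at discontinuation from the study". The schedule of assessments (Table 1 in both documents) agrees.

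SAP 6.9, Clinical Laboratory Evaluations, sets the tables. It plans descriptive statistics for baseline, for study discontinuation and for the change between them. It adds that "Shift tables in relation to the normal range from baseline to study discontinuation will be presented". The selection rule is "For post-baseline laboratory values, only scheduled values will be tabulated", followed by "Post-baseline repeat/unscheduled assessments will be disregarded, although they will be listed in the relevant appendices to the report". The same sentence goes on: "in particular all clinically significant values will be noted in a table or a separate listing". A further paragraph begins "Details of clinically warranted clinical laboratory tests and microscopic urinalysis will be provided in" and points to Appendix 16.2.

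SAP 6.2 adds a general rule: "All tabulations involving change from baseline data will only include subjects with cohort data", meaning subjects with both a baseline and a follow-up value.

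**The concern.** Laboratory results, as observed values and as changes from baseline, are a named safety endpoint in the protocol synopsis, and safety is the primary objective. A shift table limited to the exit sample describes laboratory status when subjects leave. Samples drawn between first dose and exit are taken because a physician saw a reason to test. They are the likeliest to show a transient abnormality, and the rule sets them aside.

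At stake is whether the report can say how many subjects had an out-of-range result at any time on lofexidine. Under the present rule a reader would have to rebuild that number from listings.

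**Working it through.** There is no stated figure to reproduce; this is a data-handling rule. The check compares it with the schedule.

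**1. Scheduled post-baseline time points** (Table 1, laboratory row)

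| Period | Laboratory test |
|---|---|
| Screening | Fixed |
| Baseline, Day 1 | As needed |
| Days 1-3 | As needed |
| Days 4-7 | As needed |
| Days 8-14 | As needed |
| Discontinuation/end of study | Fixed |

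There is one scheduled point after baseline, at exit.

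**2. The rule applied to a subject** with a normal baseline and an out-of-range as-needed result during treatment

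| Exit sample | Planned shift table shows |
|---|---|
| Out of range in the same direction | Normal to abnormal: counted |
| Back in range | Normal to normal: not counted |
| None | No classified shift, and no entry in the change table under SAP 6.2 |

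The third row can occur. Protocol 15.3.4 only requests the exit procedures of discontinuing subjects, and SAP 6.6 lists withdrawn consent and loss to follow-up among the reasons for leaving.

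**3. Direction.** Let A be the subjects out of range at exit and B those out of range on any as-needed test between first dose and exit. The planned table counts |A|. The number out of range at any tested time is |A ∪ B| = |A| + |B \ A|. The shortfall |B \ A| is made up of the second and third rows above and cannot be negative. As a measure of abnormality during treatment, the exit table can therefore equal or understate the count from all results, never exceed it.

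**4. Comparison within SAP 6.9.** The vital-signs section leaves repeat and unscheduled readings out of its ordinary tabulations but uses all values for the summary of potentially clinically significant readings. The laboratory section has the first half of that arrangement and not the second.

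**5. Size.** The shortfall depends on four rates: the share of subjects tested as needed, the share of those out of range, the share normalising by exit, and the share with no exit sample. None is given. Only the last can be put on a scale, by assumption. Protocol 10.1 expects about 250 to 500 treated subjects (N). With an assumed share d lacking an exit sample, N × d is:

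| d (assumed) | N = 250 | N = 500 |
|---|---|---|
| 10% | 25 | 50 |
| 20% | 50 | 100 |
| 40% | 100 | 200 |

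These are subjects without an exit value. They are not subjects with an uncounted abnormality: only those who also had an out-of-range as-needed result would be affected, and that number is unknown.

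**The case against.** The case for leaving the plan alone is substantial.

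- **Clinically significant findings have other routes.** SAP 6.9 requires them to be noted, and Protocol 16.7 makes a clinically significant laboratory abnormality an adverse event. The treatment-emergent tables give such events by preferred term with numbers and percentages.
- **Missing exit values are visible.** SAP 5.1 reports the number of non-missing observations, and SAP 5.2 the number missing in categorical tables.
- **Early leavers are covered by design.** The Table 1 footnote asks for exit procedures whenever a subject leaves, so an abnormality that leads to discontinuation will often be sampled.
- **The exit sample can be an on-treatment sample.** Subjects finishing on Day 7 leave after at least one dose that day and after the exit procedures (Protocol 14.3.2).
- **The exclusion follows the schedule and not the result.** Adding as-needed tests makes detection depend on who was ill enough to be tested. The study is single-arm and descriptive, so no comparison is biased.

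Most of this stands, and it limits the point. It does not close the gap. The adverse event route depends on the investigator's opinion in an open-label study, so values out of range but not judged significant are listed and counted nowhere. A listing alone would satisfy the clause on significant values, so no laboratory table with a denominator is assured. SAP Section 7 might settle that choice, but its table list has no entries in the public text, and nothing is held against the plan for that. The count of missing exit values does not say whether those subjects had an abnormal earlier result. The dependence on who was tested is real, and a label on the added table deals with it.

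**Conclusion.** The point holds in a limited form. As-needed laboratory results between first dose and exit do not enter the descriptive, change or shift tables. The loss is the incidence of on-treatment out-of-range values not judged clinically significant, together with an assured laboratory table that has a denominator. The direction is certain (equal or understated), but the size cannot be determined from the documents.

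A reader might infer more, and the documents do not support it:

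- That on-treatment abnormalities are left out of the report. Unscheduled values are listed, and significant ones are also noted and recorded as adverse events.
- That subjects without an exit sample disappear. They stay in the baseline statistics and listings and should appear in the missing counts.
- That no sample taken during treatment is tabulated. For Day 7 finishers the exit panel falls on a dosing day.
- That a percentage of affected subjects missed can be quoted. Any such figure would rest wholly on assumed rates of normalisation and missing samples, and would ignore the adverse event tables and listings.

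The change is still worth making: the present rule can only understate, and the data needed are already collected.

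**What to change.** In SAP 6.9, Clinical Laboratory Evaluations:

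1. Keep the baseline-to-discontinuation descriptive, change and shift tables on scheduled values.
2. Add a shift table, relative to the normal range, from baseline to the worst post-baseline value. Show the lowest and highest values separately, and use all scheduled, repeat and unscheduled results from first dose to exit. This matches the all-values rule already used for potentially clinically significant vital signs.
3. Label the table as including unscheduled tests. Report beside it the number of subjects with no post-baseline result and the number contributing only unscheduled results.

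The cost is one more table per laboratory panel, from data already in the database, with no change to trial procedures. The drawback is that as-needed tests come from sicker subjects, so the incidence shown is that among results obtained, under unequal testing. The label and the two counts make this plain.
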